10.2.3. Prior and Ongoing Therapies

All medications and procedures conducted within 30 days prior to dosing will be recorded at Screening. Updates to medications or procedures prior to study treatment administration should be made as needed.

10.2.4. Medical History

A complete medical history of each subject will be collected and documented during Screening to determine subject eligibility. The history should include disease characteristics relevant to the study (including date and details of diagnosis, associated interventional procedures and/or hospitalizations), social history (eg, tobacco use, alcohol use), recent blood donations (within 30 days), illnesses, participation in other investigational drug studies, and participation in any medical device clinical investigations.

10.2.5. Clinical Chemistry and Hematology

Select Check-in clinical chemistry and hematology assessments noted in [Appendix 1](#) and [Table 2](#) are required to be resulted for eligibility purposes prior to randomization. For those select lab assessments, laboratory assessments obtained within 48 hours prior to randomization may be referenced for purposes of assessing eligibility. For all other serum chemistry and hematology assessments, laboratory assessments collected within 60 days prior to Day 1 and with a panel relevantly similar to those listed in [Table 2](#) in the clinical judgement of the Investigator (or qualified designee) may be referenced for purposes of assessing eligibility (Section [4.2](#)).

10.2.6. Diagnostic Angiography

Confirmation of lesion and vessel characteristics is required for eligibility purposes prior to randomization. Lesion length should be measured across a distance where stenosis is at least 20% of the vessel diameter for the entirety of the lesion length. For elective PCI patients and non-urgent NSTEMI/UA patients who are undergoing PCI more than 12 hours after diagnosis, the lesion must be located in a ≥ 2.75 mm diameter coronary artery; the lesion must also be ≥ 18 mm long and require the use of one or more stents that in total must be ≥ 20 mm long; and TFG must be 2 or 3. For NSTEMI patients undergoing PCI urgently within 12 hours after diagnosis, the coronary artery diameter of the culprit lesion must be ≥ 2.75 mm and TFG must be 2 or 3. Diagnostic angiography including confirmation of lesion-related eligibility can be performed prior to randomization at Check-in or within 60 days prior to Day 1, as defined in the Schedule of Assessments ([Appendix 1](#)). In cases when diagnostic angiography is not performed at Check-in, lesion and vessel characteristics should be assessed as part of Baseline target vessel angiographic measures assessment prior to administration of study treatment. Diagnostic angiography findings used to determine subject eligibility, whether obtained within 60 days prior to Day 1 or at Check-in, must be entered in the eCRF.

10.3. Percutaneous Coronary Intervention

Cardiac catheterization using either trans-radial or femoral artery approach, coronary angiography, and PCI with predilation (if applicable) and stent deployment, will be performed in line with accepted institutional practice.

Periprocedural anticoagulation should be achieved with heparin or bivalirudin using standard institutional practice for the duration of the procedure only. Prolonging the anticoagulation treatment is permitted as bail out therapy for no reflow or acute stent thrombosis only and if done, it should be reported as a concomitant medication in the eCRF; any associated adverse events should also be reported in the eCRF.

10.4. Pharmacodynamic Assessments

10.4.1. Coronary Physiology Indices

Assessment of coronary physiology indices will be performed on all randomized subjects and will be used to characterize the PD effects of temanogrel. Indices of coronary physiology to be assessed in this study include IMR (Section [10.4.1.1](#)), coronary flow reserve (CFR) (Section [10.4.1.2](#)), and fractional flow reserve (FFR) (Section [10.4.1.3](#)). Coronary physiology indices will be assessed and analyzed as previously described ([Fearon 2000](#)) using the

Coroventis CoroFlow™ Cardiovascular System, v3.0 or later, and details on the applicable methods can be found in a separate operation manual. The coronary physiology indices will be assessed at three timepoints: Baseline values will be assessed before study treatment administration (after randomization at Baseline, unless already assessed at Check-in for confirmation of suitability for PCI per institutional standards; in that case these values can be used as Baseline values), Pre-PCI values after completion of study treatment administration, but before the PCI procedure, and Post-PCI values within 15 minutes of completion of the PCI procedure. Planned timepoints for assessment of coronary physiology indices are provided in the Schedule of Assessments ([Appendix 1](#)). Additional details regarding the procedures for collection and transfer of coronary physiology indices data will be provided in a separate operation manual.

10.4.1.1. Index of Microcirculatory Resistance

IMR will be used as a primary quantitative assessment of MVO. Briefly, IMR will be obtained using an intracoronary pressure and temperature sensor-tipped guidewire by previously described thermodilution technique ([De Bruyne 2001](#), [Pijls 2002](#)). Thermodilution curves will be obtained in triplicate from a hand-held 3 mL rapid injection of room temperature saline at baseline and after maximal hyperemia induced by 140 µg/kg/min of adenosine infused intravenously. IMR will be defined as the mean distal pressure at maximum hyperemia multiplied by the mean hyperemic transit time, as previously described ([Fearon 2003](#), [Fearon 2013](#)). IMR_{corr} (IMR corrected for the influence from collateral supply) will be calculated using the following equation, to account for the presence of significant epicardial stenosis without the need for balloon dilation to measure the coronary wedge pressure (P_w), as previously described ([Yong 2013](#)):

$$IMR_{corr} = P_a \times T_{mn} \times [1.34 \times P_d/P_a - 0.32]$$

where IMR_{corr} is IMR value corrected for the influence from collateral supply, T_{mn} is mean transit time at maximal hyperemia, P_d is mean distal coronary pressure at maximum hyperemia, P_a is mean aortic pressure at maximum hyperemia.

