10.4.1.3. Fractional Flow Reserve

The FFR will be calculated from the ratio of distal to proximal mean pressures at maximal hyperemia ($FFR = [\text{distal coronary pressure}/\text{aortic pressure at max hyperemia}]$).

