10.9. Order of Events and Priority for Timed Assessments

Every effort should be made to perform procedures as closely as possible to the scheduled times indicated in the Schedule of Assessments ([Appendix 1](#)).

On Day 1, the timing of events should first be determined by subject safety requirements and then by the scheduled times and sequential order of events as described in this protocol, giving consideration to appropriate posture conditions, practical restrictions, and the other procedures scheduled to be performed at the same timepoint. The preferred order of events in the Peri-PCI period is as follows:

1. Diagnostic angiography including confirmation of lesion-related eligibility (not required if a diagnostic angiography obtained within 60 days prior to Day 1 confirms lesion characteristics)
2. Randomization
3. Baseline peripheral blood draw
4. Baseline target vessel angiographic measures (not required to be repeated if completed during diagnostic angiography at Check-in; in cases when diagnostic angiography is not performed at Check-in, lesion and vessel characteristics should be assessed as part of Baseline target vessel angiographic measures assessment prior to administration of study treatment)
5. Baseline coronary physiology indices (IMR, CFR, FFR; not required to be repeated if completed at Check-in for confirmation of suitability for PCI per institutional standards)
6. Treatment administration
7. Post-treatment / pre-PCI peripheral blood draw (collected 0-2 minutes after the end of the IV administration of randomized study treatment)
8. Post-treatment / pre-PCI coronary physiology indices (IMR, CFR, FFR)
9. PCI with predilation (if applicable) and stent deployment
10. Post-PCI (within 15 minutes of the completion of the PCI procedure) coronary artery (coronary ostium and coronary artery distal to the lesion) blood sampling

11. Post-PCI (within 15 minutes of the completion of the PCI procedure) coronary physiology indices (IMR, CFR, FFR)
12. Post-PCI (within 15 minutes of the completion of the PCI procedure) target vessel angiographic measures
13. Post-PCI (within 15 minutes of the completion of the PCI procedure) peripheral blood draw

Specific timing of the study activities listed above is not critical (unless specified) as long as activities are completed in the order specified.

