11. PLANNED STATISTICAL METHODS

11.1. General Considerations

Details regarding the statistical analyses will be provided in a Statistical Analysis Plan (SAP), which will be finalized prior to study database lock (unblinding).

Continuous variables will be summarized using the number of observations (n), mean, standard deviation (SD), median, minimum, and maximum. Categorical variables will be summarized using frequency counts and percentages.

Unless otherwise specified, continuous endpoints will be analyzed using analysis of covariance (ANCOVA) with a model that includes treatment group and randomization stratification factor as factors and Baseline IMR value and Baseline value as covariates. Least square means, standard errors (SEs), and 95% confidence intervals (CIs) for the treatments and their difference will be presented together with their p-value.

Proportion-based endpoints will be analyzed by either the Cochran-Mantel-Haenszel method adjusting for randomization stratification factor. The number and percentage of subjects achieving the goal and the difference in proportion between treatment groups achieving the goal, along with p-value and the 95% CIs will be reported. The odds ratio relative to placebo and percentage of difference from placebo will be presented together with corresponding 95% CIs and the p-value.

Pairwise comparisons of each temanogrel treatment group compared to placebo will be conducted. In addition, analyses of the pooled temanogrel treatment groups compared to placebo will be conducted.

Where statistical assumptions (eg, normality, proportional odds) are not met, alternative approaches will be evaluated (eg, non-parametric analysis, log transformation).

Efficacy data will be analyzed by randomized treatment, while safety data will be analyzed by actual treatment received.

All secondary and exploratory analyses will be interpreted in an exploratory manner.

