11.2. Determination of Sample Size

This study is planned to randomize, treat, and complete safety, tolerability, PK, and PD assessments in approximately 99 subjects (12 in Stage A, 87 in Stage B).

It is assumed that the primary endpoint, which is the change from Baseline in IMR measured immediately after PCI, is normally distributed with a mean of 6 and SD of 3.5. Assuming a 1:1:1 randomization, 90 evaluable subjects (30 subjects in each of the 2 temanogrel treatment groups and placebo) is sufficient to achieve at least 90% power to detect a treatment effect of 3 (a clinically significant reduction of 50% from placebo) between each of the temanogrel treatment groups and placebo by a 2-sample t-test using a 2-sided significance level of 0.05.

The primary endpoint analysis will be based on pooled data from subjects in Stage A and Stage B.

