11.5. Efficacy Analyses

The primary and secondary endpoints will be analyzed using the Full Analysis Set (FAS). Other important statistical considerations such as sensitivity analyses and subgroup analyses will be described in the SAP.

The primary endpoint of the study is the change from Baseline in IMR measured immediately after PCI. The primary PD analysis will be analyzed using ANCOVA with a model that includes treatment group and randomization stratification factor as factors and Baseline IMR as a covariate. Least square means, standard errors (SEs), and 95% CIs for the treatments and their difference will be presented together with their p-values.

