11.6.1. Primary Endpoint

- Change in IMR from Baseline to Post-PCI

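### Optional precision gain: the primary ANCOVA on uncorrected IMR could also adjust for Baseline FFR, a pre-dose value already collected that partly tracks the effect of opening the lesion

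*Combined protocol and SAP*

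**What the plan says.** - **Index.** Section 10.4.1.1: "IMR will be defined as the mean distal pressure at maximum hyperemia multiplied by the mean hyperemic transit time". This is Pd x Tmn, with no correction. The same section says IMRcorr will also be calculated, "to account for the presence of significant epicardial stenosis", as Pa x Tmn x (1.34 x Pd/Pa - 0.32).
- **Endpoint.** Section 11.6.1: "Change in IMR from Baseline to Post-PCI".
- **Primary model.** Section 11.5 specifies an ANCOVA that "includes treatment group and randomization stratification factor as factors and Baseline IMR as a covariate".
- **Sizing.** Section 11.2 assumes that "the change from Baseline in IMR measured immediately after PCI, is normally distributed with a mean of 6 and SD of 3.5", with a target difference of 3 and 30 evaluable subjects per arm.
- **Timing.** Section 10.9 places "Baseline coronary physiology indices (IMR, CFR, FFR; not required to be repeated if completed at Check-in" for confirming suitability) before dosing, then the PCI, then the Post-PCI indices.
- **FFR.** Section 10.4.1.3 defines it as the "ratio of distal to proximal mean pressures at maximal hyperemia", the same two pressures that enter IMRcorr.

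Read consistently, the endpoint, the model and the sample size all refer to uncorrected IMR. In the supplied text IMRcorr appears only in the abbreviation list and Section 10.4.1.1; no endpoint or model uses it. Section 11.5 leaves sensitivity analyses to the SAP. That reached draft v0.3 and is not supplied, so nothing is said here about its content.

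**The concern.** The two readings whose difference is the primary endpoint are taken under different epicardial conditions: a stenosis at Baseline, a stent at Post-PCI. By including a correction for stenosis, the protocol accepts that a stenosis can distort uncorrected IMR. If so, part of each subject's change reflects how tight the lesion was rather than what happened in the microcirculation. That part varies between subjects with Baseline FFR, and Baseline IMR alone removes only some of it.

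Two modest things are at stake. One is precision of the between-arm contrast. The other is a clean reading of within-arm change: a true rise in microvascular resistance would be understated by about 1 to 2 units at Baseline FFR 0.80 to 0.70.

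**Working it through.** **1. The plan's own figure.** Difference 3, SD 3.5, 30 per arm, two-sided 0.05, two-sample t-test (Section 11.2): power 90.4%. The stated figure of at least 90% reproduces.

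**2. Ratio of the two indices.** With FFR = Pd/Pa,

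IMR / IMRcorr = FFR / (1.34 x FFR - 0.32) = 1 / (1.34 - 0.32/FFR).

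Assume corrected IMR 20, Post-PCI FFR 0.90 and no microvascular change. Post-PCI IMR is then 20 x 1.016 = 20.3.

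| Baseline FFR | Ratio | Baseline IMR | Change from opening the lesion |
|---|---|---|---|
| 0.80 | 1.064 | 21.3 | -1.0 |
| 0.75 | 1.095 | 21.9 | -1.6 |
| 0.70 | 1.133 | 22.7 | -2.3 |
| 0.60 | 1.240 | 24.8 | -4.5 |

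This is one part of a change that Section 11.2 assumes to be +6 net.

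**3. What a covariate can remove.** The Baseline part is IMR - IMRcorr = Baseline IMR x (0.32/FFR - 0.34). It is nonlinear in FFR and multiplied by Baseline IMR, so a linear FFR term cannot capture all of it. Across the main simulations a linear term removed about 40 to 80% of the component left after Baseline IMR. The share was as low as 24% when the slope of Post-PCI on Baseline microvascular resistance was varied, and it is smaller where Baseline FFR varies little. Variation from Post-PCI FFR, simulated independently of Baseline FFR, is not removed. Baseline IMRcorr as the covariate removed more in each of these comparisons, for example 83% against 63% with Baseline FFR 0.70 (SD 0.10) and true IMR 20 (SD 8).

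**4. Effect on precision.** Simulated with three arms of 30, a 25% elective stratum, corrected Baseline IMR 20 (SD 6) and Post-PCI FFR 0.90 (SD 0.04). The microvascular change was solved so that the uncorrected change in placebo has mean 6 and SD 3.5. All FFR and IMR distributions are assumptions.

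| Mean Baseline FFR | Variance cut, FFR SD 0.05 | Power without / with FFR | Variance cut, FFR SD 0.10 | Power without / with FFR |
|---|---|---|---|---|
| 0.85 | about 2% | not run | about 7% | not run |
| 0.80 | 2.5% | 90.1 / 90.7% | about 11% | 91.5 / 93.8% |
| 0.75 | 3.5% | 90.6 / 91.5% | about 16% | 92.3 / 95.8% |
| 0.70 | about 5% | 92.1 / 93.0% | about 26% | 94.5 / 98.5% |

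The Monte Carlo standard error on power is about 0.4 point, so the gains at SD 0.05 are barely above noise. In interval width, a 2 to 5% cut gives 1 - sqrt(0.98) = 1% to 1 - sqrt(0.95) = 2.5% narrowing. A 7 to 26% cut gives 1 - sqrt(0.93) = 3.6% to 1 - sqrt(0.74) = 14%.

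**5. Sensitivity.**
- Corrected Baseline IMR 15 (SD 5), mean FFR 0.70 to 0.85: cut 1 to 3% at FFR SD 0.05 and 4 to 14% at SD 0.10. At 25 (SD 7): 3 to 8% and 12 to 46%.
- Equation half right on average and varying between subjects (mean FFR 0.75): cut 1.0%, 2.6% and 4.3% at FFR SD 0.05, 0.08 and 0.10.
- No artefact: cut 0%, and power moves from 90.1 to 89.9% or from 90.5 to 90.0%.

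**6. Bias.** The mean treatment estimate was -2.96 to -3.03 for a true -3 under both models. In a separate null run, type I error was 4.97% without FFR and 4.99% with it.

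**The case against.** The strongest reply is that nothing fails. The contrast is unbiased, and in every main scenario above the planned model already has at least 90% power. A valid, adequately powered ANCOVA that could be somewhat sharper is a matter of covariate preference. That stands, and it is why the point is rated minor.

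The size is also set by assumption. Holding the net change at mean 6 and SD 3.5 means that a larger artefact forces a larger and less variable microvascular change. The 26% end needs about +8.6 with SD 2.6; the 46% end needs +9.3 with SD 1.96. Nothing in Section 11.2 supports those values, so the upper end should be read with caution.

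Section 11.1 gives little support for a second covariate. Its default for continuous endpoints, "Baseline IMR value and Baseline value as covariates", adds each endpoint's own Baseline value, which for the primary endpoint is Baseline IMR again.

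Three stronger readings are tempting, and the documents support none of them:
- A reader might infer that the treatment effect is biased. The component is equal in expectation across randomized arms.
- A reader might infer that the study is underpowered. Taking 3.5 as the SD of an artefact-free change would put power near 80% for mean FFR 0.70 (SD 0.10) and true IMR 20 (SD 8). But Section 11.2 attaches 3.5 to the change in IMR itself, which Section 10.4.1.1 defines as uncorrected.
- A reader might infer that IMRcorr was forgotten. A sensitivity analysis on it is just what Section 11.5 leaves to the SAP.

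**Conclusion.** The point holds as a free, minor improvement in precision. The primary model omits a pre-dose covariate which, if the protocol's equation holds, carries information about a lesion-related part of the primary change. With the 6 and 3.5 of Section 11.2 read as uncorrected IMR and corrected Baseline IMR 20 (SD 6), the residual variance falls by about 2 to 5% at FFR SD 0.05 and 7 to 26% at FFR SD 0.10, for mean Baseline FFR 0.85 to 0.70. The gain is nil without an artefact. A linear FFR term takes out a substantial part of the component, not nearly all of it.

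The within-arm issue lies outside the primary inference, and an observed rise in IMR would be conservative evidence of MVO. The Note to File of 07 October 2022 records that enrollment was terminated and lists summary tables of the coronary physiology indices, so this concerns the plan as written and not reported results.

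**What to change.** In Section 11.5, fit the primary ANCOVA with treatment, stratification factor, Baseline IMR and Baseline FFR. Baseline IMRcorr is an alternative to Baseline FFR that absorbs more if the equation holds; choose one in advance.

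As a clarification, name uncorrected IMR (Pd x Tmn) as the primary index in Sections 11.2, 11.5 and 11.6.1, and state in the SAP that the same analysis on IMRcorr is a sensitivity analysis. This would also rule out a later choice between two calculated versions of the measure. Making IMRcorr the primary endpoint is not recommended, because the primary result would then rest on the correction equation.

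The cost is a few words, one degree of freedom and no new data. Baseline FFR uses the hyperemic pressures already recorded with Baseline IMR, so it should exclude no subject who has those readings. The largest simulated loss is about 0.5 point of power, when there is no artefact.

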10.4.1.2. Coronary Flow Reserve

The coronary flow reserve (CFR) will be calculated from the ratio of baseline (resting) to hyperemic mean transit time ($CFR = [\text{mean resting transit time}/\text{mean hyperemic transit time}]$).

10.4.1.3. Fractional Flow Reserve

The FFR will be calculated from the ratio of distal to proximal mean pressures at maximal hyperemia ($FFR = [\text{distal coronary pressure}/\text{aortic pressure at max hyperemia}]$).

10.4.2. Angiographic Measures

Analysis of the target vessel angiographic measures including lesion and vessel characteristics, TFG, corrected thrombolysis in myocardial infarction frame count (cTFC), thrombolysis in myocardial infarction myocardial perfusion grade (TMPG), and quantitative coronary analysis (QCA) will be performed by a blinded central core lab and details on the applicable methods can be found in a separate operation manual. The target vessel angiographic measures will be assessed at two timepoints: Baseline values will be assessed before study treatment

administration (after randomization at Baseline, unless already assessed at Check-in as part of diagnostic angiography for lesion-related eligibility; in that case these values can be used as Baseline values) and Post-PCI values within 15 minutes of completion of the PCI procedure. Planned timepoints for assessment of angiographic measures are provided in the Schedule of Assessments ([Appendix 1](#)). Detailed instructions regarding the collection and transfer of angiographic data will be provided in a separate operation manual.

10.4.2.1. TIMI Flow Grade

The TFG, a measure of epicardial perfusion, will be graded on a standard scale from 0 to 3, with TFG Grade 0 being no perfusion and TFG Grade 3 complete perfusion ([TIMI Study Group 1985](#)).

10.4.2.2. Corrected TIMI Frame Count

The cTFC, a quantitative index of coronary flow, will be calculated based upon the number of cine-frames that the intracoronary dye requires to reach distal coronary landmarks ([Gibson 2000](#), [Kunadian 2009](#)).

10.4.2.3. TIMI Myocardial Perfusion Grade

The TMPG (also known as myocardial blush grade [MBG]), is a measure of myocardial perfusion in the capillary bed at the tissues level following contrast injection into the coronary artery. TMPG will be graded on a scale from 0 to 3, with TMPG Grade 0 being no “blush” and TMPG Grade 3 normal “blush” ([Gibson 2000](#)).

